AIM 3: Describe the relationship between treatment effect and time elapsed between stroke onset and start of treatment.

Hypothesis 3: Patients who start Arm+Hand CCFES sooner after their stroke achieve better outcomes.

Methods and Procedures

The study includes three treatment groups: 1) Arm+Hand CCFES, 2) Hand CCFES, 3) Arm+Hand Cyclic NMES. The two CCFES groups will use a stimulator that activates the muscles of the paretic upper limb in response to and with an intensity proportional to movement of the contralateral arm and/or hand. This is in contrast to the Cyclic NMES, which delivers stimulation automatically and repeatedly with preprogrammed timing and intensity. For the Hand CCFES group, paretic finger and thumb extensors will be stimulated; for the Arm+Hand CCFES and Arm+Hand Cyclic NMES groups, both the elbow and hand extensors will be stimulated. The treatment dose will be equivalent for all

groups - approximately 2 hrs per day of self-administered stimulation-mediated exercise at home plus 70 min of functional task practice twice a week in the laboratory for 12 weeks.

Subjects will be assigned to one of the 3 treatments using an adaptive randomization algorithm to minimize group imbalances on: (1) time post-stroke (< 90 days vs. \geq 90 days), (2) baseline motor status (moderate vs. severe), and (3) whether or not the pre-stroke dominant side is the paretic side. Patients with at least 10° active wrist extension, 10° active thumb abduction/extension, and 10° active extension in at least two additional digits will be considered to have "moderate" impairment, and patients with less movement than this who meet all the other motor criteria will be considered to have "severe" impairment.

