Compliance with home stimulation will be monitored with diaries and electronic data-logging. Every week, participants will be given a diary to log completion of exercise sessions. Also, the stimulator will log the date and time the unit is turned on and off and the date and time of start and completion of an exercise session. The diary will be collected weekly and compared with usage data from the stimulator in the presence of the participant at the beginning of each lab session.

Most subacute stroke patients have multiple rehabilitation needs that require intervention in addition to the study intervention. Therefore, to account for the potential confounding effect of concomitant therapies, the total number of hours of physical and occupational therapy sessions will be monitored during the entire study period. Any group imbalance in concomitant therapy will be adjusted for in the statistical analysis. The use of electrical stimulation or other experimental procedures involving the hemiparetic upper limb, changes in spasticity medication, Botulinum toxin injections to upper limb muscles, intrathecal baclofen, use of an arm sling, and use of a resting hand splint will be discouraged unless they are absolutely necessary.

All subjects will undergo assessments of upper limb impairment and activity limitation by a blinded assessor prior to treatment and at 6, 12, 20, 28, and 36 weeks. The assessments will be completed in two separate sessions (less than 7 days apart) lasting < 2 hrs each in order to avoid possible fatigue effects. Participants will receive an incentive payment of \$25 when they complete each set of follow-up assessments (i.e., at 20, 28, and 36 weeks for a total of \$75 per participant).

Outcome Measures

All subjects will undergo assessments of upper extremity impairment and activity limitation by a blinded assessor prior to treatment and at 6, 12, 20, 28, and 36 weeks (unless otherwise specified below). In addition, at the 12-week assessment a questionnaire will be given regarding device usability, treatment dosage, and treatment effectiveness. The assessments will be completed in two separate sessions (less than 7 days apart) lasting < 2 hrs each in order to avoid possible fatigue

effects. The outcome measures and procedures are:

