as lasting 12 weeks, the 6-week (mid-treatment) assessments will take place during their own week, resulting in an overall Treatment Period of 13 weeks: 6 weeks of treatment with home stimulation + lab therapy sessions, a week during which the mid-treatment assessments take place, and 6 more weeks of treatment with home stimulation + lab therapy sessions. During the mid-treatment assessment week, subjects may still undergo home stimulation exercise, with the limitation that they not do so during the 24-hour period preceding a lab assessment visit.

There are a total of 40 visits involved in this study; 2 are home visits, 38 are visits to the lab.

Visit 1. Consent and eligibility (2 hrs)

Visit 2. Baseline Assessment 1 (2 hrs)

Visit 3. Baseline Assessment 2 (2 hrs)

Visit 4. Randomization, Device Setup and Training (2.5 hrs)

Visit 5. Home equipment setup (2 hrs)

The treatment period for all 3 groups will be 13 weeks in duration (12 weeks of defined treatment + mid-treatment assessments during week 7), with the defined treatment consisting of two components:

- 1) Therapist-guided task practice performed twice a week (70-min each) in the research laboratory.
- 2) Self-administered stimulation-mediated exercise performed 10 sessions (46-60 min each) per week at home. Also, all participants will be encouraged to use their affected hand to perform tasks at home as much as possible in order to overcome "learned non-use" by creating a habit of using the affected hand."

Visits 6-17. Therapist-Guided Task Practice. (Treatment: Weeks 1-6)

Visit 18. 6-Week Outcome Assessment 1 (Mid-treatment: Assessment week 7)

Visit 19. 6-Week Outcome Assessment 2 (Mid-treatment: Assessment week 7)

Visits 20-31. Therapist-Guided Task Practice. (Treatment: Weeks 8-13)

Visit 32. Home equipment pickup (30 min)

Visit 33. 12-Week Outcome Assessment 1 (End of treatment: Week 14)

Visit 34. 12-Week Outcome Assessment 2 (End of treatment: Week 14)

Visit 35. 20-Week Outcome Assessment 1 (2 months post-treatment)

Visit 36. 20-Week Outcome Assessment 2 (2 months post-treatment)

Visit 37. 28-Week Outcome Assessment 1 (4 months post-treatment)

Visit 38. 28-Week Outcome Assessment 2 (4 months post-treatment)

Visit 39. 36-Week Outcome Assessment 1 (6 months post-treatment)

Visit 40. 36-Week Outcome Assessment 2 (6 months post-treatment)

Selection Criteria

Inclusion Criteria

- Age ≥ 21 and ≤ 80
- ≤ 2 years of first clinical hemorrhagic or nonhemorrhagic stroke

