We hypothesized that participants treated with A+H CCFES would have greater improvements in upper extremity motor function from baseline to 6-months post-treatment than participants treated with Hand CCFES or A+H cNMES. The distributions of baseline characteristics were compared in the three groups by nonparametric Kruskal-Wallis tests or Fisher's Exact tests, as appropriate, with a significance level of 0.05. For each outcome measure, we used a mixed effects modeling approach evaluating fixed effects for group, time and group by time interaction and a random intercept and slope. Least square (LS) means, calculated using model estimates and adjusted for missing values, were computed for each group at each time point. We used differences of LS means from baseline to 6 months post-treatment to estimate the within-group mean changes and between-group differences in change. We calculated 95% confidence intervals (CIs) for these point estimates; standard errors for LS means are adjusted for model covariance parameters. CIs that do not contain zero were considered to be indicative of significant changes. Effect size (Cohen d) estimates were calculated as the between-group difference in outcome variable mean divided by the common standard deviation of the outcome variable. Secondly, we hypothesized that participants who were <90 days post-stroke or had moderate hand impairment at baseline would improve more than subjects who were >90 days post-stroke or had severe hand impairment at baseline. We used a similar mixed effects modeling approach with analysis of LS means to test these secondary hypotheses for each outcome across all participants and within each group.

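### The main mixed model gives up precision by leaving baseline means free by arm and omitting the three allocation factors; secondly, its significance rule relies on one random slope across treated and untreated weeks

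*Combined protocol and SAP*

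**What the plan says.** The Statistical Analysis Plan fits, for each outcome, "fixed effects for group, time and group by time interaction and a random intercept and slope". Nothing else is listed for the main comparison. The estimate is defined this way: "We used differences of LS means from baseline to 6 months post-treatment to estimate the within-group mean changes and between-group differences in change". On uncertainty, the plan says "standard errors for LS means are adjusted for model covariance parameters", and the decision rule is "CIs that do not contain zero were considered to be indicative of significant changes". No robust standard error, residual covariance structure, second slope or sensitivity analysis is named, and the plan does not say whether time is categorical or linear.

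Methods and Procedures describes the allocation: "Subjects will be assigned to one of the 3 treatments using an adaptive randomization algorithm to minimize group imbalances on" time since stroke (split at 90 days), baseline motor status, and whether the dominant side is the paretic one. The SAP's second hypothesis is that "participants who were <90 days post-stroke or had moderate hand impairment at baseline would improve more". Two of the three factors therefore appear in the secondary models. Side dominance appears in no model.

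Assessments take place "prior to treatment and at 6, 12, 20, 28, and 36 weeks". Experimental Flow gives 12 weeks of treatment and labels the 36-week visit as 6 months post-treatment. Under Outcome Measures, the Motor Activity Log is taken only at baseline, 12 and 36 weeks.

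**The concern.** There are two issues, and the more certain one comes first.

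**Precision.** Baseline is one of the modelled visits, and the group terms let each arm have its own baseline mean. Under randomisation those means are equal in expectation, so estimating them separately discards what baseline tells us about the week-36 value. The allocation factors are also left out. If a factor predicts change, its variation stays in the standard error even though allocation has already balanced it between arms. The model-based standard error is then too large.

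**Coverage.** A single random slope assumes that each patient's departure from the arm mean is linear in time from week 0 to week 36, across the end of treatment. The contrast joins the first and last visits, so its standard error depends directly on the fitted slope variance. Because a CI excluding zero is the test, any error in coverage is an error in the 5% level.

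With complete data and categorical visit, the point estimate does not depend on the covariance. What is at stake is the width and the level of the interval.

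**Working it through.** The documents contain no sample size, SD, correlation or response curve, so there is no plan figure to reproduce. All variances below are assumptions, in units where the between-patient variance at baseline is about 1. Visit is taken as categorical, the slope as linear in weeks, and data as complete. The contrast c is week 36 minus week 0.

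**1. Common baseline mean.** With S the true 6×6 covariance, the variance ratio against the SAP's contrast is (S66 − S16²/S11) / (c'Sc).
- Gains that plateau at week 12, gain variance 0.3, residual 0.15: S11 = 1, S16 = 0.85, S66 = 1.30. The SAP variance is 1 + 1.30 − 1.70 = 0.600. With a common baseline it is 1.30 − 0.7225 = 0.5775. The ratio is 0.9625, so the CI is 1.9% narrower.
- Correlation 0.9 per visit: S16 = 0.9⁵ = 0.590. The variances are 2 − 1.181 = 0.819 and 1 − 0.349 = 0.651. The ratio is 0.795, so the CI is 10.8% narrower.
- Over the full grid, the standard error falls 0.4-7% with independent residuals, 0.6-8% with serial correlation added, and 12-24% with serial decay alone.

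**2. Allocation factors.** Assume 30 per arm, contrast variance 0.600, and a balanced two-level factor that shifts the change by d baseline SDs. Omitting it adds d²/4 to the variance.
- d = 0: SE = √(2×0.600/30) = 0.2000.
- d = 0.3: √(2×0.6225/30) = 0.2037, 1.9% larger.
- d = 0.5: √(2×0.6625/30) = 0.2102, 5.1% larger.

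In this calculation, with free baseline means, a factor main effect left the SE unchanged. Only factor by visit brought it back to 0.2000. A factor that shifts level but not change costs nothing.

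**3. Coverage.** For each assumed S, take the random-intercept-and-slope covariance V that minimises log|V| + tr(V⁻¹S). The SE ratio is √(c'Vc / c'Sc), and type I error is 2(1 − Φ(1.96 × ratio)).
- The plateau example above: √(0.544/0.600) = 0.952, type I error 6.2%.
- Correlation 0.9 per visit: √(0.924/0.819) = 1.062, type I error 3.7%.

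Grid results, with patient gain SD from 0.25 to 1 baseline SD; the last column adds serial correlation:

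| Patient-level pattern | Independent residuals | Serial, gain SD 0.25 / 0.5 / 1 |
|---|---|---|
| Linear | 5.0% | 3.6-4.9% overall |
| Plateau after week 12 | 5.2-7.2% | 3.7-5.0 / 4.1-5.8 / 5.2-6.9% |
| 80% of gain by week 6 | 5.3-10.6% | 3.8-5.4 / 4.5-7.3 / 6.5-9.9% |
| Half of gain lost | 4.7-5.0% | 3.5-5.7% overall |
| Three quarters lost | 1.0-4.8% | 3.5-4.5 / 3.4-4.3 / 1.8-3.6% |

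Serial decay alone gives 3.4-4.2%. With serial correlation and gain SD up to 0.5, the range is 3.4-7.3%. With independent residuals and gain SD 0.5, early gain reaches 8.2% and three quarters lost falls to 3.1%. Values near 10% or 1% need gains that vary as much as baseline.

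**4. Both issues together.** This simulation used minimised allocation in three arms, assumed total N of 60 and 90, and 4,000 trials per setting (Monte Carlo SE √(0.05×0.95/4000) ≈ 0.35 points). The factors explain 0 / 10 / 20% of change variance; gain SD is 0.5 for plateau and 1 for the other two patterns. Type I error under the SAP model:
- Plateau: 4.4-5.2 / 3.8-4.0 / 2.5-2.9%.
- Early gain: 9.4-9.7 / 7.5-7.6 / 5.9-6.1%.
- Three quarters lost: 2.8-3.1 / 2.1-2.4% / not run.

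Unstructured covariance with baseline and factors gave 4.6-5.6% in all 16 settings. With baseline but without the factors it gave 4.5-5.5% when they explain nothing and 2.9-4.1% when they explain 10-20%. CI width of the full repair relative to the SAP was 0.96-0.97 / 0.91 / 0.85-0.86 for plateau, 0.88 / 0.83 for three quarters lost, and 1.17 / 1.10-1.11 / 1.04 for early gain, where the SAP interval is too narrow.

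**The case against.** A random intercept and slope is a conventional longitudinal model, and nothing in the documents shows that it is wrong for this trial. That stands. A reader might infer that the SAP's interval is too narrow and its error rate inflated. The documents do not support that: the assumed patterns push coverage both ways, and a half-lost gain with independent residuals leaves it near 95%. Nor do they support the opposite comfort, that omitting predictive factors cancels any understatement. In the early-gain setting the error rate was still 7.5-7.6% and 5.9-6.1% with factors explaining 10% and 20%.

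The SAP's remark that standard errors are adjusted may denote a small-sample correction such as Kenward-Roger. It would still rest on the same covariance. The list of terms may also be incomplete: Methods and Procedures promises adjustment for imbalance in concomitant therapy, which the SAP does not list either. But nothing says that the allocation factors enter the main model, and the secondary models for two of them answer a different question.

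Three limits of the evidence also stand. Two of the three simulated patterns use gains as variable as baseline. The repair was tested as its complete-data equivalent, so convergence with missing visits was not examined. Robust standard errors were simulated only without factor effects, where they gave 4.6-5.8%. Nothing in the documents suggests that side dominance predicts change; the reason to include it is that allocation used it.

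**Conclusion.** The point holds as a should-fix of modest size. The firmer part is lost precision. Given randomisation, a common baseline mean lowered the variance in every scenario tried, by an amount that depends on the baseline to week-36 correlation. The factor terms help only if the factors predict change, which the SAP expects of two. Neither omission biases the between-arm estimate.

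The covariance point is second and conditional. If patients' own deviations are not linear across the end of treatment, or residuals are serially correlated, the significance rule may run somewhat above or below 5%, roughly 3.5-7% in moderate scenarios. Every magnitude rests on assumed variances, complete data and categorical visit, so neither direction nor size can be settled for this trial. Confidence is medium.

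**What to change.** State that visit is categorical. Constrain the arms to a common baseline mean, or adjust for baseline. Add the three allocation factors with their interaction with visit; main effects alone are not enough for a change contrast. Base the CI on an unstructured within-patient covariance with Kenward-Roger degrees of freedom. Name the fallback: if that model does not converge, keep the random-slope model with the same baseline and factor terms and use small-sample-corrected robust standard errors. Keep the contrast unchanged, as the between-arm difference in change at 6 months post-treatment.

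No new data are needed. The cost is 6×7/2 = 21 covariance parameters in place of 4 for outcomes measured at six visits (3×4/2 = 6 for the Motor Activity Log), plus the factor terms, at a sample size that the documents do not state. The SAP is written in the past tense, so the change may mean refitting analyses already run; if so, report the refit as a sensitivity analysis beside the planned one.

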We have developed Contralaterally Controlled Functional Electrical Stimulation (CCFES), an innovative neuromuscular electrical stimulation (NMES) treatment for improving the recovery of hand function after stroke. Hand CCFES stimulates the paretic hand to open in proportion to the degree of volitional opening of the contralateral unimpaired hand. This enables the stroke survivor to perform active repetitive hand opening exercises, hand motor-control tasks, and functional tasks with the paretic hand. In this study, we add stimulation of elbow extensors controlled by the contralateral elbow in order to improve reach as well as hand opening. The purpose of this study is to maximize the treatment effect of CCFES by adding stimulated elbow extension. The specific aims are to (1) estimate the effect of Arm+Hand CCFES on upper limb motor impairment and activity limitation, (2) estimate the effect of adding stimulated elbow extension to Hand CCFES, and (3) define the relationship between treatment effect and time elapsed between stroke onset and start of treatment. Stroke survivors with upper limb hemiplegia (≤ 2 years) will be randomly assigned to receive 12 weeks of either Arm+Hand CCFES (stimulates elbow extension and hand opening), Hand CCFES (stimulates hand opening), or Arm+Hand Cyclic NMES (stimulates elbow extension and hand opening but with pre-set timing and intensity, i.e., not intention-driven), plus lab-based therapist-guided task practice. Upper limb impairment and activity limitation will be assessed at baseline, 6, 12, 20, 28, and 36

weeks.

This is the first randomized controlled trial of Arm+Hand CCFES in subacute upper extremity hemiplegia. Ultimately, the information learned in this study will serve to accelerate the development of a new treatment for reducing post-stroke disability.

Specific Aims

AIM 1: Estimate the effect of Arm+Hand CCFES on upper limb motor impairment and activity limitation.

Hypothesis 1: Stroke survivors treated with Arm+Hand CCFES have better outcomes on upper limb impairment and activity limitation measures than those treated with dose-matched Arm+Hand Cyclic NMES.

AIM 2: Estimate the effect of adding stimulated elbow extension to Hand CCFES.

Hypothesis 2: Stroke survivors treated with Arm+Hand CCFES will have greater reductions in upper limb impairment and activity limitation than those treated with Hand CCFES.

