1) Box and Block Test (primary). The Box and Block test is a measure of gross manual dexterity, which requires the subject to pick up one block at a time, move it over a partition, and release it in a target area as many times as possible in a one-minute period.

2) Reaching Workspace. Subjects will be seated with their trunk restrained using a harness with straps going over both shoulders. A padded plastic forearm-wrist orthosis will be used to attach the subjects' arm to a gimbal on the end of the armature of a HapticMaster robot. The HapticMaster has a negligible amount of inertia during a reaching task and will measure the reaching workspace of the subject as he/she traces out as large a reaching area as possible (following Sukal, Exp Brain Res, 2007). The HapticMaster will be used to provide a frictionless haptic surface (i.e., a "haptic table") to simulate a table so that the reaching table workspace can be measured as well as the reaching workspace when the arm is unsupported. Reaching workspace will be measured under 4 conditions: 1) with the hand at rest and the arm fully supported, 2) with the hand at rest and the arm unsupported, 3) during attempts to volitionally open the hand with the arm fully supported, 4) during attempts to volitionally open the hand with the arm unsupported.

3) Fugl-Meyer Motor Assessment (upper extremity portion). The Fugl-Meyer Motor Assessment (FMA) is a valid and reliable measure of post-stroke motor impairment. An assessor requests the subject to attempt specific volitional movements of the upper limb (shoulder, elbow, forearm, wrist, and hand), and rates their ability to perform each movement on a 3-point ordinal scale (0, cannot perform; 1, perform partially; and 2, perform fully). The maximum score is 66 (upper limb portion).

4) Stroke Upper Limb Capacity Scale (SULCS). This test will be administered when the outcome assessments are done. The SULCS is a 10-item test in which stroke patients are rated using a 2-point ordinal scale on their performance of upper limb tasks ranging from reaching forward to manipulating coins. The SULCS takes approximately 10-15 minutes to complete.

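### The SAP does not use the protocol's primary label for Box and Block: it calls any 95% CI that excludes zero significant, for every outcome and for within-group as well as between-group change

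*Combined protocol and SAP*

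**What the plan says.** In the protocol's Outcome Measures section, the first item reads "Box and Block Test (primary", and no other item carries that tag. The list continues with reaching workspace (four conditions), the upper-extremity Fugl-Meyer, the SULCS, the Arm Motor Abilities Test, the Motor Activity Log (two ratings) and a questionnaire.

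The Specific Aims do not tie the hypotheses to one measure. Hypothesis 1 expects "better outcomes on upper limb impairment and activity limitation measures than those treated with dose-matched Arm+Hand Cyclic NMES". Hypothesis 2 states: "Stroke survivors treated with Arm+Hand CCFES will have greater reductions in upper limb impairment and activity limitation than those treated with Hand CCFES".

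The Statistical Analysis Plan hypothesises that the Arm+Hand CCFES group "would have greater improvements in upper extremity motor function from baseline to 6-months post-treatment than participants treated with Hand CCFES or A+H cNMES". It continues "For each outcome measure, we used a mixed effects modeling approach", and uses LS-mean differences from baseline to 6 months post-treatment "to estimate the within-group mean changes and between-group differences in change". It puts 95% CIs on these estimates and adds: "CIs that do not contain zero were considered to be indicative of significant changes". A similar model is used to "test these secondary hypotheses for each outcome across all participants and within each group", the hypotheses here being those on time since stroke and baseline severity. The SAP names no primary outcome and states no testing order and no multiplicity adjustment.

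**The concern.** The outcome list and the SAP do different jobs here and are not joined. The list says which measure matters most. The SAP says what will be called significant, and it does so without reference to the list. Nothing in the SAP tells a reader whether a significant Fugl-Meyer difference beside a null Box and Block difference would support Hypothesis 1, leave it unsupported, or count only as a lead for later work. Because both hypotheses are worded over impairment and activity limitation generally, they do not settle the matter either.

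The same rule also calls within-group changes significant. A change from baseline inside one arm mixes any treatment effect with spontaneous recovery, with the concomitant therapy that the protocol itself expects, and with whatever else happens over the follow-up. It has no concurrent comparison, so it cannot show a treatment effect, however narrow its interval.

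What is at stake is how the results are labelled and what may be claimed from them. Trial conduct and data are not affected.

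**Working it through.** The documents give no sample size, power or familywise error figure, so there is none to reproduce. The one fixed quantity is that a 95% CI excluding zero is a two-sided 5% test, or 2.5% in the direction that a hypothesis states.

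**Inputs**
- Contrast: baseline to 6 months post-treatment only (SAP). There is no inflation over visits.
- Number of scores K: 6 if items 1 to 6 of the outcome list give one score each; 10 if workspace conditions and Motor Activity Log ratings are counted separately (1 + 4 + 1 + 1 + 1 + 2). The questionnaire is left out: it is given at 12 weeks only and has no change from baseline. The documents do not say which count applies.
- Correlation ρ between outcomes: not in the documents. Assumed equal for all pairs, at 0.9, 0.8 and 0.5.
- Equal arms: assumed. This matters only for the joint figure at the end.

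**Chance of at least one false favourable interval, one hypothesis, no true difference**

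With z_k = √ρ·F + √(1−ρ)·e_k, where F and e_k are independent standard normals:

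P = 1 − ∫ φ(t)·[Φ((1.96 − √ρ·t)/√(1−ρ))]^K dt

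| Scores | ρ = 0.9 | ρ = 0.8 | ρ = 0.5 |
|---|---|---|---|
| 1 (Box and Block alone) | 2.5% | 2.5% | 2.5% |
| 6 | 5.4% | 6.9% | 10.4% |
| 10 | 6.4% | 8.6% | 14.4% |

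For reference, independent outcomes would give 1 − 0.975^6 = 14.1% and 1 − 0.975^10 = 22.4%.

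**The same, counting a false interval in either direction**

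| Scores | ρ = 0.9 | ρ = 0.8 | ρ = 0.5 |
|---|---|---|---|
| 1 | 5% | 5% | 5% |
| 6 | 10.8% | 13.9% | 20.7% |
| 10 | 12.8% | 17.3% | 28.7% |

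Hypotheses 1 and 2 are directional, so the first table is the one that matches support for a hypothesis.

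**Within-group intervals, as an illustration**

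Assume that every arm truly improves by the same 0.5 SD (SD of change), with 15 to 30 per arm. The chance that one arm's interval excludes zero is p ≈ Φ(0.5·√n − 1.96).
- n = 15: Φ(1.936 − 1.96) = 0.49
- n = 30: Φ(2.739 − 1.96) = 0.78

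Two such arms disagree on significance with probability 2p(1−p). That is 50% at n = 15 and 34% at n = 30, although the arms do not differ.

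**Both comparisons, Box and Block only**

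The two contrasts share the Arm+Hand CCFES arm, so with equal arms their correlation is 0.5. The chance of at least one false result is 9.1% (4.5% in favour of Arm+Hand CCFES).

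**The case against.** The strongest reply is that the plan already contains what is needed. Protocol and SAP are one combined document, one outcome is marked primary, and the SAP fixes the time contrast. A reader can put these together. The front page also says that the text was extracted from the IRB protocol, so silence here is weaker evidence than silence in a full stand-alone SAP. This stands in part: a reader might infer that the primary endpoint was dropped or contradicted, and the documents do not support that. The label is simply not used where significance is defined.

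Second, a reader might infer that the SAP lets any one significant outcome confirm a hypothesis. It does not say so. Its rule reads individual estimates, Aims 1 and 2 are worded as estimation, and effect sizes are reported. The error rates above are therefore conditional on someone accepting a single favourable outcome as support. The SAP leaves that open, and it does not prescribe it. Nor is the 11% to 21% two-sided range the chance of false support, since half of it lies in the direction that would count against the hypothesis.

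Third, the main hypothesis is explicitly comparative, so nothing says that a within-group interval decides it. That is correct. What remains is that the word significant is attached to such changes without a caveat.

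Fourth, a reader might treat the absence of joint control over the two comparisons as an error. They are stated as separate aims, so separate testing at 5% is defensible. The 9.1% describes a trade-off and does not add to this point. The subgroup hypotheses are already called secondary, although they too are tested for each outcome with no adjustment stated.

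**Conclusion.** The point holds as a gap between the outcome list and the decision rule. The SAP states a significance rule that applies equally to all outcomes and to both kinds of change, and it does not say which result decides Hypotheses 1 and 2. If any single favourable outcome were accepted as support, the false-positive chance per hypothesis would go from 2.5% to about 5% to 10% with six scores, or about 6% to 14% with ten. In two-sided terms it would go from 5% to about 11% to 21%, or 13% to 29%. These figures rest on assumed exchangeable correlations of 0.9 to 0.5 and on a count of scores that the documents leave open. The textual finding does not depend on any of these numbers. The remark on within-group intervals is a matter of design and needs no assumption.

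This should be corrected, but it does not put the trial's conduct or data in doubt.

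**What to change.** State in the SAP:

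1. Hypotheses 1 and 2 are decided by the between-group difference in Box and Block change from baseline to 6 months post-treatment: Arm+Hand CCFES against Arm+Hand Cyclic NMES for Hypothesis 1, and against Hand CCFES for Hypothesis 2.
2. All other outcomes and the subgroup contrasts are supportive and are reported as estimates with unadjusted 95% CIs.
3. Within-group changes are descriptive only.

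The sponsor should also say whether the two Box and Block comparisons are tested separately or controlled jointly. Either is acceptable. Separate testing costs no power and leaves the 9.1% joint error. Holm brings the joint error to about 4.6%. The documents give no power; as an assumed example, a comparison with 80% unadjusted power would fall under Holm to about 71% if the other comparison is truly null, or about 77% if both effects are real and equal.

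The cost is SAP wording and relabelling of results, with no new data. The downside is that fewer results can be called significant. The SAP is written in the past tense. If results have been seen, the change is one of disclosure and labelling: the report should say that this handling was not prespecified.
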